% of patients who attend at least one clinic-based cardiology follow up appointment within 4 weeks of discharge.

Outcome	Exposure(s)	Tables
OP CV F/U	Wellframe	
OP CV F/U	Wellframe + age + sex + insurance + state + DM2 + Partners PCP	

4. Comparison of Exploratory Outcomes:

30D Outcomes: All Cause Hospital, CV Hospital, All Cause ER, CV ER, CV FU and CR

A. 30 day readmission (All cause) (Cox Proportional Hazards Model)

Outcome	Exposure(s)	Tables
All Cause 30d	Wellframe	
All Cause 30d	Wellframe + age + sex + insurance + state + DM2 + Partners PCP	

B. 30 day readmission (CV related) (Cox Proportional Hazards Model)

Outcome	Exposure(s)	Tables
CV 30d	Wellframe	
CV 30d	Wellframe + age + sex + insurance + state + DM2 + Partners PCP	

C. MACE (Cox Proportional Hazards Model)

Outcome	Exposure(s)	Tables
MACE	Wellframe	
MACE	Wellframe + age + sex + insurance + state + DM2 + Partners PCP	

D. 90 day readmission (All cause) (Cox Proportional Hazards Model)

Outcome	Exposure(s)	Tables
All Cause 90d	Wellframe	
All Cause 90d	Wellframe + age + sex + insurance + state + DM2 + Partners PCP	

E. 90 day readmission (CV related) (Cox Proportional Hazards Model)

Outcome	Exposure(s)	Tables
CV 90d	Wellframe	
CV 90d	Wellframe + age + sex + insurance + state + DM2 + Partners PCP	

4. Engagement (Data from Wellframe)

Table 4.1

	90-day
Conversion Rate	
Enrolled/Total PCI	%
Enrolled/Approached	%
Average Days Enrolled	##
Average Medication Reminders	##
Average Patient Satisfaction	##
Average Clinical Messages	%
Average Days to First Message	##
Average Patient Messages Received	##
Average Patient Messages Opened	%
Average Patient Message Response	%
Average Patient Messages Sent	##
Average Patient Physical Activity	%

i. Conversion Rate (# pt enrolled in Wellframe out of # eligible)

- a. Percentage of patients enrolled / total PCI
- b. Percentage of patients enrolled / approached

Table 4.2

	30-day	90-day
Medication Adherence	%	%
Content Completion	%	%
Survey Completion	%	%
Weekly Patient Engagement	%	%
Daily Patient Engagement	%	%

Table 4.3: Predictors of Engagement: Pearson Correlation Analysis

Outcome	Exposure(s)	Figure
Daily Engagement 30d	Age + Sex + DM2 + knownCAD + HTN + HLD + MI/Elective + PAD	Correlation Matrix
Daily Engagement 90d	"	
Weekly Engagement 30d	"	
Weekly Engagement 90d	"	

Table 4.4: Sentiment Analysis (what the messages are about)

Table 4.5: Matrix of correlation between the different engagement values given by Wellframe

FIGURES:

1. Cardiac Rehabilitation Enrollment: Bar Plot (Intervention Group vs Control Group)
2. App Engagement: Bar Plot (Percentage of Days With App Engagement)
3. Outpatient Cardiac Follow Up: Bar Plot (Intervention Group vs Control Group)
4. 30-Day and 90-Day Readmission Rates: 2 Panel Bar Plot (Intervention Group vs Control Group)
5. App/Dashboard Representative Image (From Wellframe)
6. Process Outcomes: Flow chart of recruitment/enrollment.
7. Daily Engagement and Clinical Outcomes [CR Enrollment, CVFU, 30 Day Readmission, 90 Day Readmission]: 4 Panel Bar Plot (Intervention Group vs Control Group)
8. Predictors of Engagement: Correlation Matrix (Daily/Weekly Engagement Rates vs Traditional CV Risk Factors [Age, Sex, Known CAD, MI, PAD, DM2, HTN, HDL])

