- Utilization and Attendance
 - 4 Week Follow-up Appointment: % of patients who attend cardiology follow-up appointments after PCI
- **Readmission Rates**
 - **30 Days- Primary Outcome**
 - 60 Days
 - **90 Days – Secondary Outcome**
- Representation Rates (ED presentation with hospitalization)
 - 30 Days
 - 60 Days
 - 90 Days
- **Enrollment in clinic-based cardiac rehab**
 - **% of patients discharged after intervention who attend at least one session of clinic-based cardiac rehab -Secondary Outcome**
- Cost Effectiveness

[figure not shown]
Process Outcomes

These data will be provided by Wellframe to the PI. “Conversion rate” will be the primary outcome as this will indicate patient acceptability of initiating the platform and the remainder listed below will be secondary outcomes. The proportion of individuals with cardiovascular disease who accept a smartphone application upon discharge is largely an outstanding question. We hypothesize that >50% of eligible and recruited patients will enroll in the Wellframe app. Data from Wellframe will be used to assess:

- Conversion Rate: Number of patients who enroll in Wellframe app out of the number of patients eligible for participation
- Medication Adherence: % of medication reminder tasks that were completed
- Content Completion: % of content tasks that were completed
- Survey Completion: % of survey tasks that were completed
- Patient Engagement:
 - % Weekly engagement (percent of days in which patient had engaged at least once over the previous 7 days)
 - % Daily engagement (percent of days in which patient had engaged)
- Patient Messaging:
 - Number of messages sent
 - Percent of messages sent to patients that were opened at any point
 - Percent of messages sent to patients that had at least one message from the patient afterwards
- Patient Satisfaction: average response to patient satisfaction questions asked through app’s survey functionality
- Patient Physical Activity
- Clinical Messaging:
 - Total number of messages sent
 - Percent of patients who received at least one message

Primary and secondary outcomes are labeled and in bold, all other outcomes are exploratory outcomes.

Schema

■ Subject Enrollment

■ Study Procedures

■ Study Closeout and Post Study Follow-up

Subject Enrollment

Overview

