A Smartphone-based Application Post-myocardial Infarction to Manage Cardiovascular Disease Risk
NCT03416920
Version Date: 12/28/19
[name], [name]
Statistical Analysis Plan

A. Background and Rationale:

The period between inpatient hospitalization for symptomatic coronary artery disease (CAD) and post-discharge office consultation remains a vulnerable interval for adverse outcomes. We sought to develop and evaluate a tool to help guide, reassure and educate patients during this susceptible time.

We aimed to recruit and onboard 150 patients who have undergone percutaneous coronary intervention (PCI) with a novel mobile health platform developed specifically for this population. The mobile application (app) includes educational about specific procedures (PCI) and diagnoses (coronary artery disease, acute myocardial infarction) as well as lifestyle education programs (hypertension, hyperlipidemia, diabetes, weight loss, smoking cessation). The app also utilizes live health care coaches to interact with participants virtually to facilitate adherence to outpatient follow up, enrollment in cardiac rehabilitation and achieve individually targeted goals.

B. Hypothesis:

Our overall hypothesis is that engagement with our smartphone application post PCI will correlate with increased rates of enrollment in cardiac rehabilitation amongst study participants as compared to historical controls.

C. Endpoints:

- C.1. Primary:** 90-day cardiac rehabilitation enrollment rates
- C.2. Secondary:** 30-day cardiac outpatient follow up attendance

D. General Study Design and Plan

- D.1. Design:** Multi-site stratified single-arm prospective study

- D.2. Type of controls:** Historical

D.2.a. Control ascertainment: Query of Research Patient Data Registry (RPDR) database (a centralized clinical data registry that gathers clinical information from various Partners hospital systems with a query tool that provides users with detailed medical record information on identified patient populations that meet user-defined characteristics and criteria such as diagnoses, procedures, medications and/or laboratory results) for subjects aged 21-85 years old who underwent percutaneous coronary intervention from 01/01/2015 through 12/31/2017.

D.2.b. Control matching: Controls matched for Age, Sex (M/F), State (MA/non-MA), PCI Type (MI/Elective), DM2 (Y/N), Partners PCP (Y/N), Insurance Type (Commercial/Medicaid/Medicare/Other), Site (MGH/BWH)

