30-day hospitalization	Admission date to a Partners hospital within 30 calendar days of incident PCI.
90-day hospitalization	Admission date to a Partners hospital within 90 calendar days of incident PCI.
Cardiac reason for hospitalization	Admission for chief complaint of cardiac etiology (ie CAD, CHF, arrhythmia), admission requiring cardiac consultation or admission to a cardiology ward unit.
30-day ER visit	Presentation to Partners ER or Urgent Care within 30 calendar days of incident PCI without subsequent hospitalization.
90-day ER visit	Presentation to Partners ER or Urgent Care within 90 calendar days of incident PCI without subsequent hospitalization.

90-day Cardiac Rehabilitation	Attendance of cardiac rehabilitation intake session at a Partners facility within 90 calendar days of incident PCI.
30-day Cardiac Follow Up	Attendance of cardiac outpatient follow up appointment at a Partners facility (with MD or NP) within 30 calendar days of incident PCI
30-day repeat PCI	Repeat percutaneous intervention on same or new coronary lesion within 30 days of incident PCI.
90-day repeat PCI	Repeat percutaneous intervention on same or new coronary lesion within 90 days of incident PCI.
90-day Stroke	Chart diagnosis of or admission for new stroke within 90 calendar days of incident PCI as noted in Partners EHR.
90-day Nonfatal MI	Chart diagnosis of or admission for myocardial infarction (without subsequent death) within 90 calendar days of incident PCI as noted in Partners EHR.
90-day CV Death	Documentation of death within 90 calendar days of incident PCI noted in Partners EHR with cause specified as secondary to CAD, CHF, Arrhythmia or other clear cardiovascular reason.
90-day All Cause Death	Documentation of death within 90 calendar days of incident PCI noted in Partners EHR.
Conversion Rate	Number of patients enrolled in Wellframe out of number of total patients eligible for study.
Days Enrolled	Number of days between patient onboarded with Wellframe app and marked done by clinical staff.
Medication Reminders	Number of medication reminders set up by patient (0 if patient has not set up any reminders).
30-day Medication Adherence	Percentage of medication reminder tasks completed within 30 days on app. (Null if no patient reminders set up)
90-day Medication Adherence	Percentage of medication reminder tasks completed within 90 days on app. (Null if no patient reminders set up)

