D.8. Sample size and power: We have at least 95 percent power with 150 enrolled participants, 450 matched historical controls, with alpha equal to 0.05, to detect an effect of at least 2-fold increase in the primary clinical outcome, likelihood of enrollment in cardiac rehabilitation within the 90 day study period with baseline 25% enrollment rates⁶.

E. General Considerations:

E.1. Analysis populations:

E.1.a.: Full analysis population: All intervention subjects who downloaded the study application and 3:1 matched historical controls.

E.1.b.: Engagement population: All intervention subjects who downloaded the study application.

E.2. Covariates and subgroups: Sex (M/F), State (MA/non-MA), PCI Type (MI/Elective), DM2 (Y/N), Partners PCP (Y/N), Insurance Type (Commercial/Medicaid/Medicare/Other)

E.3. Missing data: Missing data values for participants who fit inclusion criteria will default to zero or “no” for dichotomous variables. Missing data values for participants will default to “unknown” or “other” for continuous or categorical variables.

F. Summary of study data: All continuous variables will be summarized using the following descriptive statistics: n (non-missing sample size), mean, standard deviation, median, maximum and minimum. The frequency and percentages (based on the non-missing sample size) of observed levels will be reported for all categorical measures. In general, all data will be listed, sorted by site, treatment and subject, and when appropriate by visit number within subject. All summary tables will be structured with a column for each treatment in the order (Control, Experimental) and will be annotated with the total population size relevant to that table/treatment, including any missing observations.

G. Protocol deviations: Subjects who do not fit inclusion criteria will be removed from the data set prior to analysis. Subjects with missing data will be treated as discussed above (Section E.3.)

H. Efficacy Analyses: The Cox Proportional Hazards model will be used to assess efficacy of the intervention (use of the application) on the primary outcome. The percentage of subjects attending cardiac rehabilitation enrollment within 90 days of discharge from incident PCI hospitalization will be compared across groups. A secondary analysis between the two groups will be conducted adjusting for covariates such as age, sex, insurance type, state, diabetes, and partners PCP).

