Primary analysis will verify balance in matching (unadjusted) via Chi-squared model for binary variables and ANOVA for categorical variables

I. Engagement Analyses: Overall engagement by patients in the intervention arm with the Wellframe application will be assessed by evaluating the number of days or weeks with at least one task completed (including surveys done, content read, activity goals reached and medication reminders used) within both a 30- and 90-day period. Individual task completion rates will also be assessed and reported within 30- and 90-day periods. Use of messaging between patients and health advocates will also be assessed during a 30- and 90-day period. Changes in these metrics across 30- to 90-days will be evaluated.

J. Exploratory Analyses:

We will compare subgroups (MI/elective) using linear regression across the 30-day engagement metrics above to evaluate predictors of engagement (adjusting for both 30-day engagement as well as matching covariates such as age, sex, PCI type, state, insurance, partners PCP and site).

We will use the Cox Proportional Hazards model to assess efficacy of the intervention on lowering rate of ER visits for cardiovascular reasons, ER visits for all causes and hospitalizations for all reasons.

We will use the Cox Proportional Hazards model to assess efficacy of the intervention on reducing rates of repeat PCI, stroke, non-fatal MI, cardiovascular cause of death and all cause death within 90 days of enrollment.

We will use the Cox Proportional Hazards model to assess for improvement in percentage of patients adhering to cardiovascular follow up appointments within 30 days of discharge.

K. Type I Error Control: We will control for error by limiting our primary outcome to 90-day cardiac rehabilitation enrollment. All subsequent analysis, including secondary outcomes, will be considered exploratory.

L. References:

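### The SAP puts the primary, the secondary and the clinical-event outcomes on conflicting clocks and does not say which one governs

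*SAP*

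**What the plan says.** **Primary (cardiac rehabilitation).** SAP C.1 gives 90 days and no starting point. D.7 starts the 90 calendar days at the incident PCI. Section H starts them at discharge: "The percentage of subjects attending cardiac rehabilitation enrollment within 90 days of discharge from incident PCI hospitalization will be compared across groups". The definition line of shell 2.A has no window and takes patients discharged after the procedure as its denominator.

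**Secondary (cardiology follow-up visit).** SAP C.2 lists "30-day cardiac outpatient follow up attendance", again with no starting point. Elsewhere there are three windows:
- D.7: "Attendance of cardiac outpatient follow up appointment at a Partners facility (with MD or NP) within 30 calendar days of incident PCI"
- Section J: "percentage of patients adhering to cardiovascular follow up appointments within 30 days of discharge"
- Shell 2.B: the percentage "of patients who attend at least one clinic-based cardiology follow up appointment within 4 weeks of discharge"

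The protocol, under Study Outcomes, adds a fourth variant: "4 Week Follow-up Appointment: % of patients who attend cardiology follow-up appointments after PCI".

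**Clinical events.** Section J fits Cox models to repeat PCI, stroke, non-fatal MI, "cardiovascular cause of death and all cause death within 90 days of enrollment". D.7 dates the same events from the incident PCI.

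**The two groups.** Under D.2 and D.5.b the controls come from a registry query of PCIs between 01/01/2015 and 12/31/2017, with follow-up to 03/2018. No enrollment date is defined for them. Under E.1.a the app group is everyone who downloaded the app. The protocol has app patients consented the day after PCI before discharge, on the day of discharge, or by phone at least a day after the procedure.

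No section ranks these definitions or states time zero for the Cox models.

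**The concern.** Two analysts could follow this SAP faithfully and report different rates from the same records, for the primary as well as the secondary. The SAP is dated 12/28/19 and D.5.a ends follow-up in 09/2019, so the choice of window stays open after the outcomes have accrued.

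The enrollment clause in Section J raises a second problem. It cannot be applied to controls as written, so the analyst must substitute another date, most readily the PCI date from D.7. If app patients were then counted from enrollment and controls from PCI, events in the first days would be left out of the app group only.

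A shared clock does not remove one related asymmetry. An app patient has to be alive to consent and download the app, and D.2 sets no matching condition on controls.

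**Working it through.** **1. The plan's own figure.** D.8 claims at least 95% power with 150 against 450, a 25% baseline, a 2-fold increase and alpha 0.05 (taken as two-sided).
- Two proportions, 50% against 25%: pooled rate = (75 + 112.5)/600 = 0.3125. Null SE = √(0.3125 × 0.6875 × (1/150 + 1/450)) = 0.0437. Alternative SE = √(0.25/150 + 0.1875/450) = 0.0456. z = (0.25 − 1.96 × 0.0437)/0.0456 = 3.60, so power is 99.98%.
- Cox model with hazard ratio 2: app rate = 1 − 0.75² = 43.75%. Events = 65.6 + 112.5 = 178. z = ln 2 × √(178 × 0.25 × 0.75) − 1.96 = 2.05, so power is 98.0%.

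The claim is met on both readings. Reading 2-fold as an odds ratio gives 93.0%, but that has nothing to do with the clock.

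**2. Clock model.** The documents give neither length of stay nor visit timing, so both are assumed. Let L be the days from PCI to discharge, taken as 1 to 7. A window of w days from discharge is w + L days from PCI. Under a constant hazard, a rate p0 by day t0 becomes p(t) = 1 − (1 − p0)^(t/t0).

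**3. Primary, t0 = 90, t = 90 + L.**

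| Rate at 90 days from PCI | L=1 | L=3 | L=5 | L=7 |
|---|---|---|---|---|
| 25% | 25.2% | 25.7% | 26.2% | 26.7% |
| 50% | 50.4% | 51.1% | 51.9% | 52.6% |

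The shift is 0.2 to 1.7 points at 25% and 0.4 to 2.6 points at 50%. Two-proportion power stays at 99.98% to 99.99%.

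**4. Follow-up visit, t0 = 30, assuming 60% attend within 30 days of PCI.**

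| Window | L=1 | L=3 | L=5 | L=7 |
|---|---|---|---|---|
| 30 days from PCI (D.7) | 60.0% | 60.0% | 60.0% | 60.0% |
| 4 weeks from discharge (2.B) | 58.8% | 61.2% | 63.5% | 65.7% |
| 30 days from discharge (J) | 61.2% | 63.5% | 65.7% | 67.7% |
| Largest minus smallest | 2.4 | 3.5 | 5.7 | 7.7 |

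With base rates from 40% to 80% the spread is about 2 to 8 points. The protocol's four weeks after PCI would give 57.5%. For a same-day discharge the two 30-day windows coincide, and only the 28-against-30-day difference remains.

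**5. If visits cluster.** Suppose visits are normal around day 28 from discharge (SD 5) with a 3-day stay. The D.7, 2.B and J windows then give Φ(−0.2) = 42%, Φ(0) = 50% and Φ(0.4) = 66%. Around day 21 (SD 7) they give 80%, 84% and 90%. Both cases let everyone attend eventually. If only 60% ever attend, the first set becomes 25%, 30% and 39%.

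**6. If the clocks differed by group.** With no true difference, counting the app group from discharge and controls from PCI would create a difference of 0.2 to 1.7 points on a 25% primary. On a 50% to 70% visit rate it would create 1.1 to 7.7 points. For the events Section J counts from enrollment no figure can be given, because the documents state no early event rates.

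**7. Which origin fits the rest of the SAP.** D.7 dates all 12 of its timed clinical outcomes from the PCI. The last control PCI is 12/31/2017, and 90 days later is 03/31/2018 (31 + 28 + 31 = 90), exactly where D.5.b ends control follow-up.

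**The case against.** The strongest reply is that this is loose drafting. D.7 is the variable dictionary. It gives a PCI clock for every timed clinical outcome and does not distinguish the groups, so controls do have a usable definition. The word enrollment may simply mean the index date: D.7 also records age and state at enrollment, both are matching variables, and for a control that can only be an index date. Many stays may be short, since the protocol expects some patients to leave on the day of the procedure. Section K makes everything beyond the primary exploratory.

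Much of this stands, and it rules out several stronger readings that a reader might infer:
- That the event comparison is biased toward the app. No section puts the groups on different clocks; the risk is conditional.
- That app patients must be event-free until consent. They must be alive, eligible and able to consent. Nothing excludes someone with an emergency visit or repeat PCI before then.
- That the visit rate swings by 24 points. The 42% to 66% range rests on an assumed visit distribution. The protocol's four-week label makes clustering plausible but gives no schedule.
- That a window was picked after seeing results. The SAP's date does not show that anyone looked.

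The reply does not settle the conflict. Nothing says D.7 overrides Sections H and J or the shells, and H is the section that specifies the primary analysis.

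**Conclusion.** The inconsistency is certain, because it lies in the current text. The primary has two starting points, the visit has three windows in the SAP plus a protocol variant, and Section J counts events from a date controls lack while D.7 counts them from PCI.

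Its size is an illustration that depends on the assumed 1 to 7 day stay, constant hazard and visit rate. If both groups share one clock, the conclusion on the primary should hardly move and power is not in question. The secondary is more sensitive because its window is short, and tight clustering near four weeks would make it more so.

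A reader might also infer that discharge is the only sound day 0. The documents do not support that: the PCI date exists in both groups and already underlies D.7 and D.5.b. What they do require is a single common origin, whichever is chosen. This should be corrected, but it does not undermine the design.

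**What to change.** - State one day 0 that exists in both groups. Use it for every clinical outcome and as time zero in all Cox models. The incident PCI date needs the fewest edits, because D.7 and D.5.b stay as they are. App-use metrics keep their own time-on-app clock.
- Give each endpoint one window: 90 days for rehabilitation and 30 days for the visit, as in C.1 and C.2. Add the origin to C.1, C.2 and shell 2.A, change Sections H and J and shell 2.B to match, and note the departure from the protocol's four-week item.
- Delete the enrollment clause in Section J.
- Limit controls to patients discharged alive, in line with the denominator in shell 2.A. This removes the in-hospital part of the survival asymmetry. Phone-consented patients enter later still, which should be stated as a limitation.
- Add a sensitivity analysis with discharge as day 0 in both groups.

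The cost is SAP wording and a small amount of extra analysis. The sensitivity analysis needs a discharge date, which D.7 does not list. For controls treated at the end of December 2017 it also needs a few days of records past 03/2018.

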PRINCIPAL/OVERALL INVESTIGATOR

[name]

PROTOCOL TITLE

A smartphone-based application post-myocardial infarction to manage cardiovascular disease risk

FUNDING

Boston Scientific

VERSION DATE

02/26/2019

I. SPECIFIC AIMS

Specific Aim 1: To recruit and onboard 100 patients sustaining a myocardial infarction and 50 patients with symptomatic coronary artery disease without myocardial infarction who have undergone PCI with the Wellframe patient engagement platform. Patients will be recruited during index cardiac hospitalization in the inpatient setting.

Specific Aim 2: To determine feasibility of inpatient onboarding of the Wellframe patient engagement platform in the setting of acute myocardial infarction. We will evaluate process outcomes, including proportion of eligible participants agreeing to participate, survey completion rates, content engagement, patient application engagement, and patient satisfaction scores.

Specific Aim 3: To assess the clinical efficacy of the Wellframe patient engagement platform post-myocardial infarction compared to matched historical controls. We will also evaluate outpatient clinic follow-up rates after hospitalization as well as cardiac rehabilitation enrollment rates (primary outcome) for all participants. We will evaluate 90-day and 30-day readmission and ED visit rates for post-myocardial infarction participants.

We hypothesize that the patient engagement platform will be an efficient method for cardiology staff to engage, follow-up, and educate patients peri-percutaneous coronary intervention (PCI) in the setting of acute myocardial infarction.

II. BACKGROUND AND SIGNIFICANCE

Public Health Significance

Myocardial infarction is a leading cause of morbidity and mortality in the United States and worldwide.^{1,2} Acute management of myocardial infarction involves pharmacological and revascularization strategies to reduce recurrent ischemic events, including cardiovascular death.^{3,4} Secondary prevention measures include adherence to guideline-based pharmacologic strategies, management of cardiovascular risk factors, diet and lifestyle counseling, and participation in cardiac rehabilitation. Both patient- and treatment-specific factors are associated with short-term adverse events.

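### The SAP's conversion table omits the eligible-patient denominator that defines the protocol's primary process outcome, and the denominator for the >50% hypothesis is ambiguous

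*SAP*

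**What the plan says.** Protocol section III, Process Outcomes, says that conversion rate "will be the primary outcome as this will indicate patient acceptability of initiating the platform". It defines the rate as "Number of patients who enroll in Wellframe app out of the number of patients eligible for participation". Just before that definition it sets the target: "We hypothesize that >50% of eligible and recruited patients will enroll in the Wellframe app". Specific Aim 2 describes the same quantity as the "proportion of eligible participants agreeing to participate".

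The SAP keeps the eligible denominator in two places. The D.7 variable list has "Number of patients enrolled in Wellframe out of number of total patients eligible for study", and item i under Engagement is headed "Conversion Rate (# pt enrolled in Wellframe out of # eligible". The two lines beneath that heading are "Percentage of patients enrolled / total PCI" and "Percentage of patients enrolled / approached", and Table 4.1 has the same two rows. The >50% target does not appear in the SAP. The SAP's figure list includes a recruitment and enrollment flow chart but does not specify its boxes.

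**The concern.** The definition and the planned output use different denominators, and the design gives reasons why the three groups will differ in size.

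- **Total PCI** includes patients who cannot qualify under SAP D.6, such as those without a smartphone or tablet or not fluent in English.
- **Eligible** includes patients who were never approached. The protocol's consent procedure says that some will have left the hospital, and that patients who received no flyer will not be called. Its close-out section treats those eligible but already discharged as a separate group for record review.
- **Approached** may leave out early refusals. The consent procedure limits approach to patients who have first given permission through a member of the care team.

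Followed as written, Table 4.1 gives no estimate of the outcome that leads Aim 2. If the two rows disagree about 50%, the plan does not say which one answers the hypothesis, so the denominator could be chosen after the data are seen.

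**Working it through.** The documents give no sample size, interval or expected count for the conversion rate, so there is no stated figure to reproduce. The only usable input is the planned enrollment of about 150 (Protocol section III). All screening counts below are assumptions.

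**Step 1: denominators side by side**

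| Place | Denominator |
|---|---|
| Protocol, Process Outcomes, definition | eligible |
| Protocol, Process Outcomes, >50% hypothesis | eligible and also recruited (undefined) |
| SAP D.7 | eligible |
| SAP item i, heading | eligible |
| SAP item i, lines a and b; Table 4.1 | total PCI; approached |

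No planned row uses the denominator of the definition.

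**Step 2: where the 50% line falls.** With 150 enrolled, a rate exceeds 50% only if its denominator is below 150 / 0.5 = 300.

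**Step 3: how the rows relate.** If every approached patient is eligible, then

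enrolled/eligible = (approached/eligible) × (enrolled/approached),

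and enrolled/total PCI ≤ enrolled/eligible ≤ enrolled/approached. The two planned rows bracket the defined rate. They settle the 50% question only when both fall on the same side of 50%. With 150 enrolled and assumed counts:

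| PCI / eligible / approached | of PCI | of eligible | of approached |
|---|---|---|---|
| 1000 / 500 / 250 | 15.0% | 30.0% | 60.0% |
| 600 / 360 / 252 | 25.0% | 41.7% | 59.5% |
| 600 / 270 / 243 | 25.0% | 55.6% | 61.7% |

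The outer columns fall on opposite sides of 50% in all three cases. The defined rate fails in the first two and passes in the third.

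**Step 4: sensitivity to the fraction approached.** Assume 60% of approached patients enroll. If 60, 70, 80 or 90% of eligible patients are approached, the defined rate is 0.6 × 0.6 = 36%, 0.7 × 0.6 = 42%, 0.8 × 0.6 = 48% or 0.9 × 0.6 = 54%. It passes 50% only if more than 0.5 / 0.6 = 83% are approached.

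**Step 5: one case with intervals.** Take 250 approached, 70% of those eligible, so 250 / 0.7 = 357 eligible. Wilson 95% intervals: 150/250 = 60% (54-66%); 150/357 = 42% (37-47%).

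**Step 6: when the ordering fails.** The protocol allows patients to be approached in the cath lab before eligibility is confirmed. Assume 300 approached, of whom 240 prove eligible, and no other eligible patients. Then 150/300 = 50.0% of approached and 150/240 = 62.5% of eligible, so the approached row is the lower one.

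**The case against.** The strongest reply is that enrolled/approached may be what the hypothesis intends. The hypothesis adds recruitment to eligibility, the stated purpose is acceptability, and Aim 2 speaks of agreeing. A patient who was never approached has neither accepted nor declined, so counting that patient as a non-conversion measures reach. This stands as a fair reading of the hypothesis. It does not reconcile the table with the definition, which has eligible patients alone as its denominator in both documents. Nor is the approached group a clean acceptability denominator if refusals given to the care team fall outside it.

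A reader might infer more than the documents support:

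- **That the >50% hypothesis will be wrongly declared met.** This presumes that all eligible patients are its denominator, and the wording leaves that open.
- **That enrolled/approached always overstates the defined rate.** Step 6 shows that this need not hold.
- **That the defined rate cannot be obtained from the planned output.** The flow chart may show the eligible count, though nothing requires it to.
- **That the protocol expects heavy loss before approach.** It says only that some patients will have left, and it adds flyer and telephone recruitment for early departures.

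Two further points stand. SAP section K makes everything except 90-day cardiac rehabilitation enrollment exploratory, and no test or sample size depends on the conversion rate. The screening database holds potentially eligible patients, and the documents do not say how device ownership would be established for those never contacted, so the eligible count may be only partly known.

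**Conclusion.** The mismatch is real and visible in the text: the definition uses eligible patients, and neither planned percentage does. The primary process outcome is therefore not reported as defined, and the denominator for the >50% hypothesis is ambiguous. The actual discrepancy cannot be computed from the documents. The gap between 60% and 42% follows from assuming 250 approached patients, 70% of those eligible, with approached a subset of eligible. It shows that the choice of denominator can decide the answer, not that it will in this trial. The effect is confined to feasibility reporting under Aim 2; no confirmatory error rate is affected. The change should be made because it is cheap and removes a choice that could otherwise be made after seeing the data.

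**What to change.** 1. Add an enrolled/eligible row to Table 4.1 and item i, with n/N and a 95% CI, and label it as the conversion rate. Keep the other two ratios as supportive.
2. Require the eligible and approached counts in the planned recruitment flow chart.
3. Define eligible by one reconciled set of criteria. Protocol section III requires a long-term provider in Massachusetts or accessible records; SAP D.6 does not. State how screened patients with unknown device ownership are counted.
4. Define approached, covering patients who refuse through the care team, patients who are contacted only by flyer or telephone, and patients who are approached before eligibility is confirmed.
5. State in advance which denominator the >50% hypothesis uses, and align the protocol wording with it.

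The cost is one table row and a few sentences. The protocol already creates a database of potentially eligible patients and reviews the records of those eligible but discharged, so no new data collection is evident. The downsides are that the reported rate may be lower and that eligibility data for uncontacted patients may be incomplete. The number with unknown status should be shown.
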